1. OVERALL SYNOPSIS OF THE CLINICAL INVESTIGATION

Clinical investigation title:	Performance of Masimo INVSENSOR00057 in Detecting Atrial Fibrillation (Afib)
Study objective(s):	The objective of this study is to gather data to validate the performance of Masimo INVSENSOR00057 in detecting atrial fibrillation.
Investigational device(s):	Masimo INVSENSOR00057
Number of subjects:	Approximately 100 subjects.
Inclusion criteria:	
 • Subject is 18 years of age or older. • Subject is confirmed to have active atrial fibrillation at the time of enrollment.
Exclusion criteria:	
 • Subject is confirmed to have concurrent active arrhythmias (e.g., PVCs, bradycardia, etc.) at the time of enrollment. • Subject is allergic to adhesives or ECG gel. • Subject whose skin is not intact in or at the vicinity of the device placement site.
Duration of the clinical investigation:	The expected duration of study enrollment is 1 to 3 months.
Study endpoint(s):	Sensitivity and specificity of Masimo INVSENSOR00057 Afib detection function

2. IDENTIFICATION AND DESCRIPTION OF THE INVESTIGATIONAL DEVICE

Masimo Corporation is the developer of noninvasive technologies for the measurement and monitoring of physiological variables, such as arterial oxygen saturation (SpO₂), total hemoglobin concentration (SpHb), carboxyhemoglobin concentration (SpCO), methemoglobin concentration (SpMet), and other physiological variables to improve patient outcomes and reduce cost of care.

Masimo INVSENSOR00057 is a standalone wearable health monitor that combines the functionality of a pulse oximeter monitor and sensor into a single portable device that fits on a user's wrist. The device allows continuous monitoring of multiple parameters, including oxygen saturation (SpO₂), pulse rate (PR), respiration rate (RR), as well as an electrocardiogram (ECG) function that includes atrial fibrillation detection. The device pairs via Bluetooth to a Masimo smartphone application that provides continuous health data to the user.

[figure not shown]

Figure 1: Masimo INVSENSOR00057

3. JUSTIFICATION FOR THE DESIGN OF THE CLINICAL INVESTIGATION

There are an estimated 46 million individuals suffering from atrial fibrillation, the most common type of cardiac arrhythmia characterized by high frequency of the atrium. Patients with atrial fibrillation have approximately a 4-fold increased risk of mortality compared to the general population (Lee et al., 2018). In addition to increased risk of death, atrial fibrillation also

increases risk of heart failure and stroke. The imminent risks of stroke can be mitigated with prompt administration of anticoagulants (Piazza et al., 2018).

Certain populations are more vulnerable to atrial fibrillation than others; studies have indicated that risk factors for increased risk include older age, sedentary lifestyle, obesity, smoking, diabetes mellitus, hypertension, and obstructive sleep apnea (Staerk et al., 2018). Detecting atrial fibrillation in its early stages can significantly reduce the high disability and mortality rate. A study reviewing the prevalence of atrial fibrillation in 2009 estimated that 700,000 cases were undetected, comprising 13.1% of all cases; half of these projected cases of undiagnosed atrial fibrillation were at increased susceptibility to stroke (Turakhia et. al, 2018).

The intent of this study is to validate the performance of Masimo INVSENSOR00057 in detecting atrial fibrillation. The standard for diagnosis of atrial fibrillation is use of an electrocardiogram (ECG); advancement of this technology, especially via wearable technology, for early detection can improve the prognosis for patients and enable them to seek medical care before the arrhythmia progresses into more adverse complications.

4. BENEFITS AND RISKS OF THE INVESTIGATIONAL DEVICE, CLINICAL PROCEDURE, AND CLINICAL INVESTIGATION

4.1. Anticipated Benefits

There will be no direct benefits to the enrolled subjects. Other possible benefits would be to society as a whole. Development of new ECG technologies could enable users to monitor and identify potentially life-threatening conditions more appropriately.

4.2. Risks/Discomforts Associated with Participation in the Clinical Investigation

The following risks/discomforts associated with study procedures are anticipated adverse events. All adverse events will be documented and reported following procedures outlined in this document.

The noninvasive device used in this study are similar in technology and design to commercially available wearable noninvasive devices. There is a risk of discomfort to the subject's wrist from the device, which may include temporary skin irritation, skin inflammation, itching skin, or discomfort associated with exposure to the device, as well as potential temporary mechanical irritation or discomfort. If there are any cuts and/or abrasions near the application site, the subject will be excluded from the study to avoid any discomfort.

5. OBJECTIVES OF THE CLINICAL INVESTIGATION

The objective of this study is to gather data to validate the performance of Masimo INVSENSOR00057 in detecting atrial fibrillation. The noninvasive ECG measurements will be compared to results obtained from an FDA-cleared ECG monitor.

6. DESIGN OF THE CLINICAL INVESTIGATION

6.1. General

This is a prospective, nonrandomized, single arm study. The study endpoints are designed to validate the performance of Masimo INVSENSOR00057 in detecting Afib. The validation of the Afib detection function in the investigational device may be determined using data collected from this study, in addition to data from other Masimo sponsored studies.

The primary endpoint of this study will be the analysis of sensitivity and specificity of Masimo INVSENSOR00057 Afib detection function when compared to data collected using an FDA-cleared ECG monitor.

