6.3. Subjects

Inclusion Criteria

- Subject is 18 years of age or older.
- Subject is confirmed to have active atrial fibrillation at the time of enrollment.

Exclusion Criteria

- Subject is confirmed to have concurrent active arrhythmias (e.g., PVCs, bradycardia, etc.) at the time of enrollment.
- Subject is allergic to adhesives or ECG gel.
- Subject whose skin is not intact in or at the vicinity of the device placement site.

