6.4. Procedures

6.4.1. Recruitment and Pre-Screening

Subjects will be recruited from local clinics or cardiology offices. Subjects who present with active atrial fibrillation during their regular doctor visit will be recruited for the study.

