6.4.3. Data Collection Procedure

6.4.3.1. The subject will be seated and/or lying-in supine position and should refrain from excessive movement during the study. Subject medical history and demographic information including age, sex, skin pigmentation, ethnicity, height, and weight may be recorded for data analysis and/or subject safety monitoring purposes.

6.4.3.3. INVSENSOR00057 will be placed on the subject's wrist according to the Investigator's Brochure. [REDACTED]

[REDACTED] The device may be repositioned, as needed, to ensure proper placement.

The site of device placement should be assessed throughout the duration of the study. If there are any signs of loss of skin integrity and/or loss of circulation or perfusion, the device should be repositioned. In the unlikely event of emergency

defibrillation, the device must be removed prior to defibrillation.

6.4.3.4. [REDACTED]

6.4.3.5. Upon successful placement and Bluetooth pairing of the device, data collection will be initiated [REDACTED]
[REDACTED]
[REDACTED]

6.4.3.6. The subject will be requested to take manual ECG measurements on the INVSENSOR00057 [REDACTED]
[REDACTED]
[REDACTED]

6.4.3.7. Observations may be recorded on the case report form (e.g., subject position, timing and duration of manual measurements on the INVSENSOR00057 device).

6.4.3.8. At the conclusion of the procedure, the electrodes and device will be removed.

[REDACTED]
[REDACTED]

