7.2. Sample Size

Analysis methods consistent with Receiver Operating Characteristics (ROC) curves will be used. Therefore, the sample size was determined to meet simultaneous requirements for both Sensitivity and Specificity. The PASS 2019 software package was used to calculate the appropriate sample size using the Confidence Intervals for One-Sample Sensitivity and Specificity module. [REDACTED]

[REDACTED]

[REDACTED]

[REDACTED]

[REDACTED]

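### Specificity is half of the primary endpoint, but the visible design enrols and analyses only subjects in AFib, so this study's own data cannot estimate it

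*Combined protocol and SAP*

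**What the plan says.** The synopsis gives the study endpoint as "Sensitivity and specificity of Masimo INVSENSOR00057 Afib detection function". Section 6.1 repeats it as the primary endpoint: "The primary endpoint of this study will be the analysis of sensitivity and specificity of Masimo INVSENSOR00057 Afib detection function". Section 7.2 adds that "the sample size was determined to meet simultaneous requirements for both Sensitivity and Specificity", and 7.3.2 sets out a two-by-two table with a reference column for recordings without AFib.

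The population is described as follows:

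- Section 6.1: "This is a prospective, nonrandomized, single arm study".
- Section 6.3, inclusion: "Subject is confirmed to have active atrial fibrillation at the time of enrollment". Section 6.4.2 requires every subject to satisfy all the inclusion criteria.
- Section 6.4.1: "Subjects who present with active atrial fibrillation during their regular doctor visit will be recruited for the study".
- Section 7.3.1 removes from the analysis subjects who entered with AFib but whose waveforms, on medical review, do not fit that diagnosis.

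Section 6.1 also says that validation of the AFib function "may be determined using data collected from this study, in addition to data from other Masimo sponsored studies".

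**The concern.** Specificity is estimated from people or recordings that the reference calls negative. The visible plan neither recruits nor admits anyone expected to be negative, and its exclusion rule then removes subjects who prove to be negative by chance. Followed as written, the study can answer only the sensitivity half of its primary question.

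Two consequences follow. First, the study alone could not tell a good detector from one that labels every trace as AFib. Second, the visible text does not tie specificity to a named external dataset. If that dataset were chosen after the AFib results were known, the specificity claim would be post hoc. The documents do not say that this will happen; the visible text simply does not prevent it.

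**Working it through.** **Inputs from the documents.** About 100 subjects (synopsis); one arm (6.1); active AFib required of all (6.3, 6.4.1); enrolled subjects whose ECG is not AFib excluded (7.3.1); 1 − specificity = FP/(FP + TN) (7.3.2). The inputs to the 7.2 sample size calculation are redacted, so the figure of about 100 cannot be reproduced. The point does not depend on it.

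**Step 1: the denominator.** Reference-negatives = N × (1 − prevalence). With prevalence 1 in the analysed set, 100 × (1 − 1) = 0. So FP + TN = 0, and FP = TN = 0.

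**Step 2: the measures in 7.3.2.**

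| Measure | With FP = TN = 0 |
|---|---|
| Specificity, false alarm rate | 0/0, undefined at any N |
| Accuracy | (TP + 0)/(TP + 0 + FN + 0) = sensitivity |
| PPV | Constant if TP > 0: TP/(TP + FP) = 1; with the numerator printed in 7.3.2, FP/(TP + FP) = 0 |

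A ROC analysis of these data would likewise have no false-positive axis.

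**Step 3: a device that always calls AFib.** TP = 100, FN = 0: sensitivity 100/100 = 100% and accuracy 100/100 = 100%. With 100 negatives added, all misclassified, accuracy is 100/200 = 50%.

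**Step 4: what about 100 AFib subjects do support.** Exact (Clopper-Pearson) 95% intervals for sensitivity, with one result per subject and assumed results because the plan's expected values are redacted:

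- 95/100: 88.7% to 98.4%
- 98/100: 93.0% to 99.8%

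**Step 5: could incidental negatives fill the gap?** Section 6.4.3.6 says "The subject will be requested to take manual ECG measurements on the INVSENSOR00057", and 7.3.2 counts events, so a subject with mixed rhythm might yield a negative recording. That would be unplanned. Section 7.3.1 does not say whether one discordant tracing or all of them triggers exclusion. If n independent negatives are all classified correctly, the exact two-sided 95% lower limit is 0.025^(1/n). Assuming 5 to 10 such subjects were kept:

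- n = 5: 0.025^(1/5) = 0.478
- n = 10: 0.025^(1/10) = 0.692

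**Step 6: the size a companion dataset would need.** The acceptance values are not given (7.1 refers to sponsor specifications), so these targets are illustrative. With every negative classified correctly, the smallest n for a lower limit of at least 90% is 36 (0.025^(1/36) = 0.903); for at least 95% it is 72 (0.025^(1/72) = 0.950). Any misclassified negative raises these numbers.

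**The case against.** The strongest defence is that this study was meant to supply only the AFib positives, with section 7 describing a combined analysis. Section 6.1 allows data from other sponsor studies. Section 7.4 speaks of sample size by group. The exclusion in 7.3.1 is worded for those who presented with AFib, a qualifier that would be unnecessary if nobody else were in the analysis. The text that follows the sample size sentence in 7.2 is redacted, and so are parts of 6.4.3; a comparison group or a named dataset could be there.

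Some of this stands. It cannot be said that no companion dataset exists, or that the overall validation lacks negatives, and the 7.2 calculation cannot be judged beyond its visible sentence. The plan also promises only methods consistent with ROC curves, so the ROC remark is secondary.

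The defence does not remove the conflict. The sentence on other studies is permissive and concerns validation of the function; the next paragraph still makes specificity an endpoint of this study. A second group within this study would contradict the visible single-arm statement and the inclusion criterion. If the redacted text names an outside dataset, the source of negatives is settled, but the synopsis and 6.1 would still need to agree with it.

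**Conclusion.** The concern holds, and it must be fixed before analysis. On the visible text, this study plans 0 reference-negatives among about 100 subjects. Its own data therefore cannot estimate specificity at any sample size, and accuracy and PPV say nothing beyond sensitivity. Sensitivity is estimable with useful precision.

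The count of zero follows from the unredacted eligibility, recruitment and exclusion rules. The intervals rest on assumed results and on one independent result per subject; the numbers of negatives rest on illustrative targets. The conclusion concerns this study's data alone and makes no claim about data held elsewhere.

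**What to change.** Choose one of the following.

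1. **Sensitivity only.** In the synopsis and 6.1, restate this study's primary endpoint as sensitivity. In 7.2, say that about 100 subjects support sensitivity. Remove specificity, false alarm rate, PPV, accuracy and ROC methods from what this study alone will conclude.
2. **Pooled specificity.** State in 6.1 and 7.2 that specificity is a pooled endpoint. Before analysis, identify the companion non-AFib dataset and its number of negatives.

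Either route needs an amendment signed by the principal investigator and the sponsor and approved by the IRB (section 9). Option 1 adds no subjects but narrows the stated endpoint. Option 2 keeps the endpoint but depends on a suitable dataset, which the visible documents do not identify; if one is already named in redacted text, aligning the wording may be enough.

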6.2. Investigational device(s) and comparator(s)

The study will collect data to validate the performance of the Afib detection function of INVSENSOR00057 as compared to a FDA-cleared ECG monitor.

6.3. Subjects

Inclusion Criteria

- Subject is 18 years of age or older.
- Subject is confirmed to have active atrial fibrillation at the time of enrollment.

Exclusion Criteria

- Subject is confirmed to have concurrent active arrhythmias (e.g., PVCs, bradycardia, etc.) at the time of enrollment.
- Subject is allergic to adhesives or ECG gel.
- Subject whose skin is not intact in or at the vicinity of the device placement site.

6.4. Procedures

6.4.1. Recruitment and Pre-Screening

Subjects will be recruited from local clinics or cardiology offices. Subjects who present with active atrial fibrillation during their regular doctor visit will be recruited for the study.

6.4.2. Consenting and Screening

The investigator shall not enroll any subject to participate in the study or consent any subject prior to receiving IRB approval of the informed consent form.

Following identification of a potential eligible subject as defined by the inclusion or exclusion criteria, the subject will be approached by the study staff. Study staff will explain the purpose and procedures of the study with respect to potential risks and benefits, and clarification of the subject's rights and privacy information. Ample time will be given to review the consent form. The research team will emphasize that participation is voluntary and declining participation in the study will not result in any penalty or loss of benefits that the subject is otherwise entitled.

Once the subject's questions have been answered and the consent documents are signed and dated, the Principal Investigator or delegate will also sign the informed consent documents, approving that the subject will be enrolled in the study. The investigator shall retain the original copy of the signed informed consent documents in each subject's records and provide a copy to the subject. No study related activities will be conducted until the consent form is signed.

Subjects will be screened to determine eligibility for study enrollment. Subjects must meet all inclusion criteria and none of the exclusion criteria to participate in the study. All subjects screened will be documented on the Screening and Enrollment Log. Subjects who do not meet the eligibility criteria will be considered screen failures and the reason for the status of screen failure will be documented on the Screening and Enrollment Log.

6.4.3. Data Collection Procedure

6.4.3.1. The subject will be seated and/or lying-in supine position and should refrain from excessive movement during the study. Subject medical history and demographic information including age, sex, skin pigmentation, ethnicity, height, and weight may be recorded for data analysis and/or subject safety monitoring purposes.

6.4.3.3. INVSENSOR00057 will be placed on the subject's wrist according to the Investigator's Brochure. [REDACTED]

[REDACTED] The device may be repositioned, as needed, to ensure proper placement.

The site of device placement should be assessed throughout the duration of the study. If there are any signs of loss of skin integrity and/or loss of circulation or perfusion, the device should be repositioned. In the unlikely event of emergency

defibrillation, the device must be removed prior to defibrillation.

6.4.3.4. [REDACTED]

6.4.3.5. Upon successful placement and Bluetooth pairing of the device, data collection will be initiated [REDACTED]
[REDACTED]
[REDACTED]

6.4.3.6. The subject will be requested to take manual ECG measurements on the INVSENSOR00057 [REDACTED]
[REDACTED]
[REDACTED]

6.4.3.7. Observations may be recorded on the case report form (e.g., subject position, timing and duration of manual measurements on the INVSENSOR00057 device).

6.4.3.8. At the conclusion of the procedure, the electrodes and device will be removed.

[REDACTED]
[REDACTED]

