7.3. Statistical Analysis**7.3.1. Exclusion**

The following subjects will be excluded from data analysis:

- Subjects where the paired reference or test ECG did not provide readable ECG waveforms as determined by medical personnel.
- Subjects who presented as having Afib at the time of enrollment, but who provided ECG waveforms with characteristics inconsistent with an Afib diagnosis (as determined by medical personnel).

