7.3.2. Afib Classification Accuracy Calculations

Classification accuracy will be measured by Sensitivity and Specificity as defined below.

Test \ Reference	AFIB	No AFIB
AFIB	TP	FP
No AFIB	FN	TN

$$Sensitivity = \frac{TP}{TP + FN}$$

$$FalseAlarmRate = 1 - Specificity = \frac{FP}{FP + TN} = \frac{FP}{TotalNegativeEvents}$$

$$PPV = \frac{FP}{TP + FP} = \frac{FP}{TotalPositiveDetections}$$

$$Accuracy = \frac{TP + TN}{TP + FP + FN + TN}$$

Analysis methods consistent with Receiver Operating Characteristics (ROC) curves will be used.

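### Do several manual ECG measurements per subject make the sensitivity and specificity intervals too narrow?

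*Combined protocol and SAP*

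**What the plan says.** The synopsis plans "Approximately 100 subjects". Under the data collection procedure, 6.4.3.6 states: "The subject will be requested to take manual ECG measurements on the INVSENSOR00057". The rest of that item is redacted. Item 6.4.3.7 gives, among the observations that may be noted on the case report form, "timing and duration of manual measurements on the INVSENSOR00057 device".

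Section 7.2 says that "the sample size was determined to meet simultaneous requirements for both Sensitivity and Specificity", and that PASS 2019 was run "using the Confidence Intervals for One-Sample Sensitivity and Specificity module". The inputs that would follow are redacted.

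Section 7.3.1 opens with "The following subjects will be excluded from data analysis". Its first item removes a subject when the paired reference or test ECG, in the singular, cannot be read.

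Section 7.3.2 gives a two-by-two table and the accuracy ratios. The denominator of the false alarm rate is labelled as a total of negative events and that of PPV as a total of positive detections. The sensitivity formula carries no such label. The section does not say whether a table entry is a subject or a recording, and it names no interval method. Section 7.1 refers acceptance to the sponsor's specifications and gives no figure.

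**The concern.** The plural in 6.4.3.6 and the event wording in 7.3.2 can be read as a table filled with recordings, several from each subject. Recordings from one wrist in one sitting share signal amplitude, contact quality and rhythm, so a device that misses AF once in a subject is likely to miss it again. A one-sample binomial interval assumes independent observations. Applied to pooled recordings it would be too narrow, and subjects with more recordings would weigh more in the estimate.

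Sensitivity and specificity form the primary endpoint. If the sponsor's specification is set on an interval bound, a device could appear to meet it on precision that the data do not have.

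**Working it through.** **The plan's own figure.** The 100 subjects can be neither reproduced nor refuted, because the expected proportions, interval width, confidence level and prevalence are not visible. Several assumed sets for a two-sided 95% interval come close:

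- proportion 0.85, total width 0.15, Clopper-Pearson: n = 99
- proportion 0.90, total width 0.12, Wald: 4 × 1.96² × 0.90 × 0.10 / 0.12² = 96.04, so n = 97
- proportion 0.95, total width 0.12, Wald: n = 51, or 102 in all if half the observations are reference-positive

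So 100 is compatible with a plain count of subjects. This shows consistency only; it does not prove the unit.

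**Size of the effect if recordings were pooled.** Let m be recordings per subject and ICC the within-subject correlation of correct classification. Neither is visible, so both are assumed, as is a true proportion of 0.90.

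- Design effect: DE = 1 + (m − 1) × ICC
- Naive half-width: 1.96 × √(0.90 × 0.10 / (100m))
- True half-width: naive × √DE
- Coverage of a nominal 95% interval: 2Φ(1.96/√DE) − 1
- Effective sample size: 100m/DE

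For m = 3 and ICC = 0.5:

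- DE = 1 + 2 × 0.5 = 2.0
- naive half-width = 1.96 × √(0.09/300) = 3.4 points
- true half-width = 3.4 × 1.414 = 4.8 points
- coverage = 2Φ(1.386) − 1 = 83.4%
- effective sample size = 300/2 = 150

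| m | ICC | DE | Naive half-width (points) | True half-width (points) | Coverage | Effective n |
|---|---|---|---|---|---|---|
| 1 | any | 1.0 | 5.9 | 5.9 | 95.0% | 100 |
| 2 | 0.2 | 1.2 | 4.2 | 4.6 | 92.6% | 167 |
| 2 | 0.8 | 1.8 | 4.2 | 5.6 | 85.6% | 111 |
| 3 | 0.5 | 2.0 | 3.4 | 4.8 | 83.4% | 150 |
| 5 | 0.3 | 2.2 | 2.6 | 3.9 | 81.4% | 227 |
| 5 | 0.8 | 4.2 | 2.6 | 5.4 | 66.1% | 119 |

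**Is the study too small?** For ICC up to 1, DE is at most 1 + (m − 1) = m, so 100m/DE is at least 100. If the 100 from 7.2 counts subjects, repeated recordings can only add information. Every true half-width in the table is at or below the 5.9 points that one result per subject gives. The only possible harm is a wrongly computed interval.

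**Does the plan commit to that interval?** Three readings of the text bear on this.

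1. The one-sample method appears in 7.2 for sample size. Section 7.3.2 prescribes no interval, so no naive interval is planned in the visible text.
2. The event and detection labels rename FP + TN and TP + FP. They are ordinary classifier terms and fit one result per subject equally well. They do not appear in the sensitivity formula.
3. Section 7.3.1 drops subjects and speaks of one paired ECG. With pooled recordings one would expect unreadable recordings to be dropped instead.

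**The case for a change.** The strongest reply is that 7.3.2 shows no redaction mark and still says nothing about the unit, the interval or repeated measurements. Redaction in 6.4.3.6 and 7.2 may hide the number of recordings, but it does not explain that silence. The plural appears twice in visible text. If a subject has several recordings and only one is unreadable, 7.3.1 does not say whether the recording or the subject is dropped. One sentence would settle all of this at almost no cost.

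The silence is real, and so is the arithmetic given its assumptions. But silence on the unit is missing detail; it is not a rule that gives a wrong result. The plural does not show that more than one measurement per subject enters the table, since extra ones could be retakes or practice. The redacted text is where the number and use of measurements could be stated, and it cannot be counted as absent. Unequal weighting also depends on pooling and on unequal counts, neither of which is shown.

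Nor is it free to require a single recording per subject. In the example with three recordings, the half-width would go to 5.9 points, against 4.8 when all recordings are used with correct clustering.

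**Conclusion.** The concern does not hold as a fault in the plan. That precision is overstated would need two things the visible text does not show: several recordings per subject entering the table, and an interval that treats them as independent. If both were true, intervals would be too narrow by √DE. Over the assumed cases with two to five recordings, that factor runs from √1.2 = 1.10 to √4.2 = 2.05. With one result per subject, or an interval clustered by subject, there is no loss of validity, and precision is no worse than planned, provided the planned 100 counts subjects.

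What remains is a gap that an analyst fills in the usual way: one pre-set result per subject with an exact binomial interval, or all recordings with a subject-level bootstrap or a GEE with robust variance. Both are valid and neither conflicts with anything written. The conclusion would change if the redacted parts of 6.4.3.6 or 7.2 showed that the sample size counts recordings, or that recordings are to be pooled under a simple binomial interval.
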